9.2 SAMPLE SIZE DETERMINATION

This study aims to examine the efficacy of rTMS for the treatment of AVH in schizophrenia. To determine the effect of rTMS, this study uses an exploratory approach and should be considered a pilot study. If a treatment effect of rTMS (as compared to sham rTMS) would be detected, then this may serve as the basis for a follow-up study in a larger sample.

Previous meta-analyses (Aleman et al., 2007; Demeulemeester et al., 2012; Freitas et al., 2009; C. W. Slotema et al., 2014; C. W. Slotema et al., 2010; Tranulis et al., 2008) reported effect sizes ranging from 0.42 to 1.04 for LF rTMS over the left TPJ for the treatment of AVH. Based on this, we assume an effect size of 0.9 as a clinically meaningful effect to justify rTMS for the treatment of AVH compared to conventional antipsychotic medication. Following from this, we performed an *a priori* power analysis using the statistical software package R 3.1.3 and pwr.t.test (based on (Cohen, 1988)). With the assumed effect size of 0.9 and 80% power ($\alpha = 5\%$) we will have to recruit 40 patients in total, with 20 patients in the real rTMS and 20 patients in the sham rTMS group.

Considering the limited time frame of one year and based on the investigators' experience in the clinic about the number of subjects, we expect the aim of $N = 40$ to be feasible.

9.3 POPULATIONS FOR ANALYSES

Data of all patients who attended pre-MRI and interview, 4 sessions of rTMS, and post-MRI and interview will be included in the analysis.

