1 PROTOCOL SUMMARY

1.1 SYNOPSIS

Title: Boost rTMS for AVH – Therapeutic Response and Neurobiological Prediction Markers in Auditory Verbal Hallucinations

Study Description: This is a randomized, placebo controlled, double-blind clinical trial. We aim to examine the efficacy of repeated transcranial magnetic stimulation (rTMS) for the treatment of auditory verbal hallucinations (AVH) in patients with schizophrenia who are not taking antipsychotic medication. We employ a novel, accelerated protocol with only 4 sessions of low-frequency rTMS in one day. The effects of this accelerated protocol will be compared to the sham stimulation. Additionally, we will examine the effects of rTMS on a neurophysiological level by evaluation mechanism of action in the temporo-parietal lobe.

Objectives: Primary Objective:
Examine the efficacy of low-frequency rTMS for AVH in patients with a schizophrenia spectrum disorder.

Secondary Objectives:
Examine the effects of rTMS on the quality of AVH, positive symptoms, general psychopathology, and the global level of functioning of these patients. Last, confirm that rTMS has no side effects on cognitive functioning.

Determine the neuroimaging-related biomarkers associated with response to rTMS using the baseline imaging parameters (rCBF, resting fMRI, T1, and DTI) to predict response to rTMS treatment. Further,

compare pre- and post-treatment imaging parameters (rCBF, resting fMRI, T1, and DTI) to characterize rTMS effects on AVH.

Endpoints:

Primary Endpoint:

- AVH assessed using the Hallucination Change Scale (HCS) at baseline (first visit), after the last TMS session, after the post-MRI.

Secondary Endpoints:

- a) Assessment of the qualitative content of hallucinations will be assessed using the revised Beliefs About Voices Questionnaire (BAVQ-R)
- b) Assessment of AVH as part of positive symptoms will be assessed with the Brief Psychiatric Rating Scale (BPRS)-subscale that includes "Hallucinatory Behavior", "Conceptual Disorganization", "Suspiciousness", and "Unusual Thought Content".
- c) Global functioning will be assessed using the Clinical Global Impression (CGI) and General Assessment of Functioning (GAF) questionnaires.
- d) Cognitive functioning will be assessed using the Repeatable Battery for the Assessment of Neuropsychological Status (rBANS).

Neurophysiological changes using magnetic resonance imaging (MRI) are investigated as predictors for rTMS treatment response.

Study Population:

N = 40

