- There are no known long-range risks.

MRI

Immediate risks

- The risks of fMRI scanning are minimal. There is no ionizing radiation involved in MRI, and there have been no documented significant side effects of the magnetic fields and radio waves used on the human body to date.
- People have been harmed in MRI machines when they did not remove metal objects from their clothes or when others left metal objects in the room. All necessary precautions will be taken to prevent inadvertent presence of metal objects in the MRI room.
- Some subjects, even those without known history of claustrophobia may experience discomfort or even panic attacks in the enclosed setting of the magnet. All efforts will be taken to first calm subjects down and next to decide together with the participant whether or not to continue study participation. All subjects are informed that they can discontinue the procedure at any time, and receive instructions before scanning about communicating with the scanning system operators, which can be done either by a squeeze bulb kept in the subject's hand, or by voice through a microphone mounted inside the bore of the magnet, if they feel uncomfortable. Although, these scans are being done for research purposes, the images from the MRI will be reviewed by a physician who normally reads such images (such as a neuroradiologist). As a result, the subject will be informed of any unexpected findings. If our research yields any information that can be relevant in the subject's clinical management, we will notify them.

The occurrence of the MRI procedure and the subject's study participation may be documented in their medical record.

Long-range risks

- However, because the effects of strong magnetic fields on a fetus are not well documented at this time, pregnant women will be excluded from the study. Pregnancy is assessed with a pregnancy test prior to the two MRI measurements. People have been harmed in MRI machines when they did not remove metal objects from their clothes or when others left metal objects in the room.

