6.4 STUDY INTERVENTION COMPLIANCE

Compliance to study intervention is firstly confirmed by the patient signing the informed consent form. If patients do not want to continue treatment and finish all 4 rTMS sessions together with pre- and post-imaging and interviews, they will be excluded from the study which will be mentioned in the case report form. The data collected up to this point will not be included in the analysis because the primary outcome is the outcome measure of the HCS for which all three measures (baseline, after the last rTMS session, post-MRI) are necessary to reasonably estimate the symptom trajectory.

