8 STUDY ASSESSMENTS AND PROCEDURES

8.1 EFFICACY ASSESSMENTS

Rating

All assessments will be performed by trained raters.

Time frame

Screening procedures / evaluation must be done on the same day or the day before inclusion of the patient into the study. The reason for this is that we assess rTMS effect independently of potentially influencing antipsychotic medication effects. Therefore, patients cannot start with antipsychotic medication treatment parallel to the rTMS treatment. Clinical interviews will be conducted by trained staff.

Imaging

MRI acquisition will consist of the following: On the day of imaging, the patient will be transported to the North Shore University Hospital 3T Siemens Prisma MRI suite. The patient will undergo an approximately 55 minutes long acquisition session. All subjects will receive structural (e.g., T1) and functional (e.g. resting BOLD fMRI, DTI, and ASL) MRI exams. During the anatomical images, the participating subject will be asked not to move, during resting state fMRI, the subject will be asked to open their eyes and to think of nothing in particular, but to stay awake. The total scanning time will be approximately 55 minutes.

Assessment of instruments

The primary outcome measure is the improvement of AVH measured with the HCS.

The secondary outcome measures are:

- Qualitative outcome of the BAVQ-R
- AVH as part of positive symptoms measured with the respective BPRS-subscale
- Global functioning assessed using the CGI and GAF
- Cognitive functioning assessed using the rBANS

Structural and functional neurophysiological characteristics are investigated as predictors for rTMS treatment response.

Outcome criteria

Responder criteria:

- a. Clinically significant improvement is defined as a score of <8 on the HCS (Hoffman et al., 2013)
- b. Drop-outs: defined as patients who discontinue treatment before completing the 4 rTMS sessions.

Premature exits:

- a. Consent for study participation is withdrawn before 4 rTMS treatments have been administered, or
- b. rTMS is discontinued for clinical or other reasons before 4 rTMS have been administered, or
- c. Patient misses more than two treatments in total.

Both drop-outs and premature exits in this study will be analyzed as last observation carried forward.

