9.4 STATISTICAL ANALYSES

9.4.1 GENERAL APPROACH

Descriptive statistics will include all patients who completed the study. Patient groups (stratified according to either their sham or real rTMS treatment) will be compared concerning age, sex, socio economic status, general psychopathology (CGI, GAF), severity of AVH (BPRS-subscale, BAVQ-R), and cognitive outcome (rBANS). In particular, mean (standard deviation) together with the range (min, max) will be assessed for the two groups.

Inferential statistics: the p-value will be set to 5% and therefore every value below this threshold is considered significant. Effect sizes will be calculated as well to evaluate if we are dealing with a clinically important effect. Covariates will be included in the analyses such as age and sex.

General assumptions of heterogeneity and normality will be assessed before any subsequent analysis. Based on this either parametric or non-parametric tests will be chosen.

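### Sections 9.3 and 6.4 admit only patients who attend the second MRI to the primary HCS comparison, although the HCS does not need that scan

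*Combined protocol and SAP*

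**What the plan says.** Section 9.3 gives one population for all analyses: "Data of all patients who attended pre-MRI and interview, 4 sessions of rTMS, and post-MRI and interview will be included in the analysis". Section 6.4 says that patients who do not finish the sessions, both scans and the interviews are excluded, and that their data are not analysed. Its reason is that the primary outcome is the HCS, "for which all three measures (baseline, after the last rTMS session, post-MRI) are necessary to reasonably estimate the symptom trajectory". The synopsis (1.1) sets the same three time points: "AVH assessed using the Hallucination Change Scale (HCS) at baseline (first visit), after the last TMS session, after the post-MRI".

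Other sections bear on this rule:

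- Section 3 anchors the HCS on the patient's own account and sets the baseline score at 10. No imaging enters the score.
- The schema (1.2) lists the final clinical interview and the post-treatment MRI as separate items of Visit 4.
- Section 6.1.2 uses the baseline scan to locate the stimulation target. The second scan has no such role.
- Section 7.2 replaces treated patients who withdraw or are withdrawn.
- Section 8.1 applies LOCF to drop-outs and premature exits, both defined by stopping or missing treatment sessions.

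**The concern.** Take a patient who receives all 4 sessions, is rated on the HCS after the last one, and then does not have the second scan. This patient was randomised, was fully treated and has primary outcome data, but is left out because of an event after treatment that the endpoint does not depend on.

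Missing the scan could well be related to clinical state. These are inpatients not taking antipsychotics. For imaging, "the patient will be transported to the North Shore University Hospital 3T Siemens Prisma MRI suite", and the session lasts about 55 minutes. Section 2.2.1 recognises that some "may experience discomfort or even panic attacks in the enclosed setting of the magnet". Section 7.2 also ends participation for worsening that is treated with antipsychotics and for suicidal or homicidal risk. If this happens between session 4 and the scan, a post-treatment HCS already collected is discarded.

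If such loss is related to outcome and differs by arm, the analysed groups are no longer the randomised groups. Replacement brings the count back to 40 but not the comparability, and a report of 40 completers would not show that anyone was lost.

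**Working it through.** **1. Does any clause keep this patient in?**

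- 9.3: no, the second scan was not attended.
- 6.4: no, imaging is unfinished, so the data collected are not analysed.
- 8.1 (LOCF): does not apply, because all 4 sessions were given.
- 9.4.1 and 9.4.3: no help. Descriptive statistics cover study completers, and the secondary analyses leave out drop-outs.
- 7.2, read with 6.4: the patient is replaced.

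No other population or sensitivity analysis is defined. Because every patient has 10 at baseline, only two ratings carry outcome information. This patient has at least one of them.

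**2. The plan's own figure.** Section 9.2: "we assume an effect size of 0.9 as a clinically meaningful effect"; "With the assumed effect size of 0.9 and 80% power", alpha 5%, two-sample t-test, 20 per arm. Sidedness is not stated.

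- Normal approximation, two-sided: n = 2(1.960 + 0.842)² / 0.9² = 2 × 7.85 / 0.81 = 19.4, so 20 per arm and 40 in total.
- Exact t: 20.39 per arm. Power with 20 per arm is 79.2%.
- One-sided: 16 per arm, so the stated 40 is a two-sided figure.

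The stated size reproduces. It contains no allowance for loss.

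**3. Effect of selective loss with replacement.** The documents give no missed-scan rate, so these are assumptions. One arm enrols 20 + k patients and loses k (2 or 3); the other loses none; 20 per arm are analysed. The HCS is in SD units, lower is better. The k patients lost are those highest on a latent tendency to miss the scan that has correlation ρ with a worse outcome. The test is a two-sided t-test at 5%.

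Shift in the mean difference = ρ × (k/20) × m, where m is the expected mean of the k highest of 20 + k standard normal values: 1.68 for 2 of 22, 1.54 for 3 of 23.

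- k = 2, ρ = 0.5: 0.5 × 0.10 × 1.68 = 0.08 SD
- k = 3, ρ = 0.5: 0.5 × 0.15 × 1.54 = 0.12 SD
- k = 3, ρ = 1: 1 × 0.15 × 1.54 = 0.23 SD

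Rejection rates come from 400,000 simulated trials per row.

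| Lost (k) | ρ | Shift (SD) | False positives, real-arm loss, d = 0 | Power, sham-arm loss, d = 0.9 |
|---|---|---|---|---|
| 2 | 0.3 | 0.05 | 5.4% | 74.9% |
| 3 | 0.3 | 0.07 | 5.7% | 73.1% |
| 2 | 0.5 | 0.08 | 6.1% | 72.1% |
| 3 | 0.5 | 0.12 | 6.9% | 69.1% |
| 2 | 1 | 0.17 | 9.8% | 66.5% |
| 3 | 1 | 0.23 | 13.5% | 60.5% |

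Real-arm loss exaggerates the benefit; sham-arm loss masks it. If instead the lost patients come from the first 20 and every replacement completes the scan, the two worst-case rows become 9.4% and 12.5% false positives, and 66.6% and 61.0% power. Across both versions the worst case is about 9-14% and 61-67%.

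**4. Loss without selection.** With equal loss in both arms the mean difference is unbiased. With random loss (ρ = 0) and replacement, power stays at 79%. The cost is recruitment: 40 / 0.90 = 44.4, so 45 randomised at 10% loss; 40 / 0.85 = 47.1, so 48 at 15%.

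**The case against.** The case for leaving the rule alone has substance. The trial describes itself as an exploratory pilot. Section 8.2 keeps out patients with significant claustrophobia and offers a mock scanner, and everyone who could miss the second scan has already completed the first. A patient given antipsychotics for worsening leaves the study under 7.2 whether or not a scan was due, so dropping the MRI condition would not recover that patient's Visit 4 rating. All this makes the group lost because of the scan alone smaller. It does not justify discarding the rating taken after the last session, and with 20 per arm two or three exclusions matter.

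A reader might infer four stronger things that the documents do not support:

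- *That ordinary loss cuts power from 79% to 75% or 72%.* Those are the values for 18 and 17 per arm without replacement (74.6% and 72.1%). Section 7.2 replaces treated withdrawals.
- *That every excluded patient has complete outcome ratings.* The third HCS is placed after the scan, so an unscanned patient may lack it. Equally, it is too strong to say that this rating has no defined time, because Visit 4 is scheduled.
- *That the 9-14% error rate is the expected one.* It needs loss in one arm only, with exactly the worst patients missing the scan.
- *That the noise or stress of the scan distorts the third HCS.* Section 2.2.1 links voices to stress in general terms. Both arms are scanned, so this is not in itself a difference between real and sham.

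**Conclusion.** The point holds. Sections 9.3 and 6.4 make a post-treatment imaging visit a condition for entering the primary clinical comparison, and nothing else in the plan brings the excluded patients back. Usable randomised outcome data are lost, and the comparison is open to selection that replacement would hide.

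The size is uncertain. With one-arm loss of 2 to 3 per 20 and correlation 0.3 to 0.5, the effect is modest: about 5-7% false positives, or power of about 69-75% against 79%. Correlation 1 is the worst case. The documents fix neither the direction nor the size of any bias, and none arises in the mean difference if the arms lose patients equally. The reason to act is that the correction is cheap and must be made before unblinding, since choosing the population afterwards would not be credible.

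**What to change.** - **9.3 and 6.4:** remove second-MRI attendance as a condition for the HCS and the other clinical endpoints. Include randomised patients with at least one post-treatment HCS, as randomised, whether or not they were scanned. Keep the two-scan requirement for the imaging analyses only.
- **9.4.1:** align the descriptive statistics with this population.
- **9.4.2:** replace the repeated-measures ANCOVA by a likelihood-based repeated-measures model (MMRM), so that a missing third rating does not delete the patient. This assumes that missingness depends only on observed data, such as the rating after the last session; say so.
- **1.1, 1.2 and 6.4:** define the third HCS by visit (Visit 4 follow-up), so that it is collected whether or not the scan takes place. State one order of rating and scan for all patients; at present the synopsis and 6.4 put the rating after the scan, while the schema lists the interview first.
- **Reporting:** give exclusions and replacements by arm with reasons, and show the two-scan completers as a sensitivity analysis.

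The cost is wording in these sections and a little more modelling work, with no extra visit. Clinical and imaging analyses may have slightly different numbers of patients.

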9.4 STATISTICAL ANALYSES

9.4.1 GENERAL APPROACH

Descriptive statistics will include all patients who completed the study. Patient groups (stratified according to either their sham or real rTMS treatment) will be compared concerning age, sex, socio economic status, general psychopathology (CGI, GAF), severity of AVH (BPRS-subscale, BAVQ-R), and cognitive outcome (rBANS). In particular, mean (standard deviation) together with the range (min, max) will be assessed for the two groups.

Inferential statistics: the p-value will be set to 5% and therefore every value below this threshold is considered significant. Effect sizes will be calculated as well to evaluate if we are dealing with a clinically important effect. Covariates will be included in the analyses such as age and sex.

General assumptions of heterogeneity and normality will be assessed before any subsequent analysis. Based on this either parametric or non-parametric tests will be chosen.

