9 STATISTICAL CONSIDERATIONS

9.1 STATISTICAL HYPOTHESES

Primary Efficacy Endpoint(s):

H0: Real rTMS has no superior effect over sham rTMS in reducing severity of AVH in schizophrenia (HCS score).
H1: Real rTMS has a superior effect over sham rTMS in reducing severity of AVH in schizophrenia (HCS score).

Secondary Efficacy Endpoint(s):

1. H0: Real rTMS has no superior effect over sham rTMS in reducing quality of AVH in schizophrenia (BAVQ-R score).
H1: Real rTMS has a superior effect over sham rTMS in reducing quality of AVH in schizophrenia (BAVQ-R score).
2. H0: Real rTMS has no superior effect over sham rTMS in reducing positive symptoms including AVH in schizophrenia (BPRS-subscale).
H1: Real rTMS has a superior effect over sham rTMS in reducing positive symptoms including AVH in schizophrenia (BPRS subscale).
3. H0: Real rTMS has no superior effect over sham rTMS in reducing severity of general psychopathology in schizophrenia (CGI score).
H1: Real rTMS has a superior effect over sham rTMS in reducing severity of general psychopathology in schizophrenia (CGI score).
4. H0: Real rTMS has no superior effect over sham rTMS in reducing global functioning in schizophrenia (GAF score).
H1: Real rTMS has a superior effect over sham rTMS in reducing global functioning in schizophrenia (GAF score).
5. H0: Real rTMS compared to sham rTMS does not impact cognitive functioning (RBANS).

H1: Real rTMS compared to sham rTMS does not impact cognitive functioning (RBANS).

6. H0: Response to rTMS is not predicted by neurophysiological characteristics.

H1: There are specific neurophysiological markers that predict response to rTMS.

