9.4.3 ANALYSIS OF THE SECONDARY ENDPOINT(S)

Our secondary goal is to test if rTMS improves also the quality of AVH (BAVQ-R), positive symptoms (BPRS-subscale), general psychopathology (CGI), and global functioning (GAF). Further, we want to confirm that rTMS has no impact on cognitive functions (rBANS).

Therefore, we will compute a number of repeated ANCOVAs with time of measurements as the within-subject factor, group (treatment vs. placebo) as between subject's factor, and baseline BAVQ-R scores, the positive symptom BPRS-scale, the CGI, and GAF scores as covariates, respectively. Patients who drop out of the study will not be included in the analyses. Further, we will compare the rBANS scores of baseline with the outcome scores within patients.

Additionally, we want to test if baseline neuroimaging biomarkers can predict response to rTMS. Therefore, voxel-wise multiple regression analyses in our neuroimaging measures will be performed to reveal areas and networks which correlate with the baseline scores of the HCS. We will calculate structural and functional connectivity analyses.

Preprocessing, and overview of the neuroimaging measures:

Baseline metabolic neuronal activity

The treatment effect will be monitored by assessing the baseline resting metabolic neuronal activity measured by ASL (Philipp Homan et al., 2011; Kindler et al., 2012; Orosz et al., 2012). Additionally, variations in resting CBF may be used as covariates of nuisance in all the analysis steps described so far.

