To investigate the structural properties of GM and WM the 3D structural T1 and DTI measurements will be used. T1 images will be used to define the regions of interest (ROI) for both structural and functional connectivity analyses. The ROIs will comprise cortical regions in the STG and superior temporal sulcus (STS, Brodmann areas/BA 41, 42 and 52) and in the subcortical thalamic area (medial geniculate body of thalamus/MGB).

With regard to structural connectivity analyses, diffusion tensor images will be used to compute fractional anisotropy (FA) values for further use in a voxel-wise statistical analysis, which will be conducted using Tract-Based Spatial Statistics (TBSS) (Smith et al., 2006); part of FSL (Smith et al., 2004) (version 5.0). FA maps are created by fitting a tensor model to the raw diffusion data using the FMRIB diffusion toolbox. Subsequently, a brain extraction tool will remove all non-brain parts of the image (Smith, 2002). All subjects’ FA data will be coregistered to a 1 mm × 1 mm × 1 mm Montreal Neurological Institute (MNI) standard space. This step will be performed using a non-linear registration tool FNIRT (FMRIB’s Non-Linear Image Registration Tool), which uses a B-spline representation of the registration warp field (Rueckert et al., 1999). Additionally, a mean FA image will be created and thinned in order to create a mean FA skeleton that represented the centers of all tracts common to the group. A lower FA threshold of 0.2 will be used to prevent the inclusion of non-skeletal voxels (Smith et al., 2006). Each subject’s aligned FA data will then be projected onto this skeleton. The resulting data will be analyzed using voxel-wise cross-subject statistics including a randomization tool, which is a simple permutation program that allows modeling and inferences within the framework of GLM-setup and is based on non-parametric inference methods (Nichols & Holmes, 2002).

Concerning functional connectivity analyses, the ROIs will be used as seed regions to compute the functional connectivity from these regions to other cortical brain regions using the Conn toolbox, a MATLAB-based cross-platform mapping software (www.nitrc.org/projects/conn). Further, GM analyses will be performed using voxel-based morphometry (VBM) (Good et al., 2001). VBM will be computed within the statistical parametric mapping (SPM8: <http://www.fil.ion.ucl.ac.uk/spm/>). Cortical thickness will be estimated using FreeSurfer (<http://surfer.nmr.mgh.harvard.edu>).

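### Imaging hypothesis 6 is tested voxel by voxel with no multiplicity correction stated, on a regressor (baseline HCS) that is identical for every patient

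*Combined protocol and SAP*

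**What the plan says.** - **Threshold.** Section 9.4.1, under inferential statistics: "the p-value will be set to 5% and therefore every value below this threshold is considered significant". No other significance threshold appears in Section 9.
- **Hypothesis.** Section 9.1 lists imaging prediction as secondary hypothesis 6, with its own H0 and this H1: "There are specific neurophysiological markers that predict response to rTMS". The synopsis (Section 1.1) speaks of using "baseline imaging parameters (rCBF, resting fMRI, T1, and DTI) to predict response to rTMS treatment".
- **Test.** Section 9.4.3: "voxel-wise multiple regression analyses in our neuroimaging measures will be performed to reveal areas and networks". The same sentence says that these areas and networks are to be those correlating with baseline HCS scores.
- **Baseline HCS.** Section 3 anchors the scale by giving each patient's own baseline description the value 10. Only later ratings can move, between 0 and 20.
- **Inference tool.** For the FA skeleton (tract-based) analysis, Section 9.4.3 names "a simple permutation program that allows modeling and inferences within the framework of GLM-setup", based on non-parametric methods. It does not say whether the resulting p-values are corrected for the number of voxels. Nothing comparable is given for perfusion, voxel-based morphometry, cortical thickness or connectivity.
- **Exploratory status.** Sections 5.5 and 9.2 call the whole trial an exploratory pilot. Section 9.4.9 (Exploratory Analyses) is marked not applicable, so hypothesis 6 is not set apart from the others.

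**The concern.** A voxel-wise analysis produces thousands of p-values per map. A cut-off of 5% on each one controls the error for a single voxel, not for the question whether any region predicts response. Section 9.4.3 fixes details as fine as the smoothing kernel and the lower FA limit, yet leaves open the threshold that decides what counts as a finding. If the only written rule is followed, a map with no true association will still show significant areas. A positive result on hypothesis 6 would then carry almost no information.

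The second defect is in the same sentence of Section 9.4.3. Prediction of response needs an outcome that differs between patients, and baseline HCS does not differ. Correcting the regressor alone would make the test possible but would leave its false-positive rate uncontrolled, so both need attention together.

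**Working it through.** **1. The plan's own figure.** Section 9.2 gives 40 patients, "with 20 patients in the real rTMS and 20 patients in the sham rTMS group", for a standardised effect of 0.9 and 80% power at 5%. The normal approximation gives 2 × (1.960 + 0.842)² / 0.9² = 19.4, so 20 per arm. The exact two-sided t calculation gives 21 per arm, with 79.2% power at 20. The figure is reproduced within rounding. It concerns the clinical comparison and says nothing about the imaging hypothesis.

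**2. The regressor as written.** A regression slope is Σ(x − x̄)(y − ȳ) / Σ(x − x̄)². With x = 10 for every patient, numerator and denominator are both 0. The slope cannot be estimated and no p-value exists. Steps 3 to 6 therefore apply only once a varying response measure replaces baseline HCS, as hypothesis 6 requires.

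**3. False-positive chance with k effective independent tests.** Under a global null, P(at least one p < 0.05) = 1 − 0.95^k.

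| k | Chance of at least one false positive |
|---|---|
| 4 | 18.5% |
| 20 | 64.2% |
| 59 | 95.2% |
| 60 | 95.4% |
| 90 | 99.0% |
| 500 | >99.99% |

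**4. How large k is.** The plan gives no voxel count. It does give a 6 mm smoothing kernel for the perfusion images (Section 9.4.3), which is (0.6 cm)³ = 0.216 cm³ per resolution element. The search volume is an assumption:

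- 50 cm³: 50 / 0.216 ≈ 231
- 100 cm³: 100 / 0.216 ≈ 463
- 600 cm³: 600 / 0.216 ≈ 2,778

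All are well above 59. Real images may be smoother than the kernel alone. For 50 cm³ to hold only 59 elements, each would need 50 / 59 = 0.85 cm³, a smoothness of about 9.5 mm. For 600 cm³ it would need 10.2 cm³, about 22 mm.

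**5. Simulation with smooth null images.** Settings: 6 mm smoothness (from the plan), 2 mm voxels (assumed), two-sided voxel-wise correlation with an unrelated outcome.

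| Block | Runs per n | Any p<0.05, n = 20 | Any p<0.05, n = 40 |
|---|---|---|---|
| 4 cm³ (512 voxels) | 300 | 98.3% | 99.7% |
| 33 cm³ | 100 | 100% | 100% |
| 262 cm³ | 20 | 100% | 100% |

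Between 4.7% and 5.0% of voxels were flagged on average in every setting. The count in step 4 is conservative: 4.096 / 0.216 ≈ 19 elements would predict 1 − 0.95^19 = 62%, against the simulated 98%.

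**6. What correction does.** With Bonferroni correction over voxels, the simulated chance of any false positive fell to between 1% and 2.3% in the two smaller blocks. In the largest block it was 1 of 20 and 2 of 20 runs, too few to distinguish from 5%. Correction within each map still leaves multiplicity across maps. Four independent maps each held at 5% give 1 − 0.95⁴ = 18.5%. Bonferroni across the four modalities in the synopsis would use 0.05 / 4 = 0.0125 per map.

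**The case against.** **The plan is silent; it does not rule correction out.** This stands. The rule in Section 9.4.1 is generic, and the variables named around it are demographic and clinical. A corrected p-value is also a p-value judged at 5%. A reader might infer that the plan requires uncorrected voxel testing and so makes a false marker certain. The documents do not support that; the near-certainty is conditional on uncorrected use. Silence is still a defect, because it lets the threshold be chosen after the maps are seen.

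**Permutation is already named.** Only for the FA data, and without saying whether its output is corrected. It could supply the remedy but does not yet do so.

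**Not every imaging analysis tests hypothesis 6.** This stands. The test described for the resting-state networks compares conditions, and Section 9.4.3 does not say that morphometry, cortical thickness or seed connectivity will be related to response. The temporal and thalamic regions of interest are defined for connectivity and are not described as a mask for the voxel-wise regressions. The figures above need only one voxel-wise map.

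**One voxel would not be called a marker.** A reader might infer that a single flagged voxel satisfies H1. Section 9.1 gives no decision rule, and Section 9.4.3 looks for areas and networks, so this is not established. The absence of any rule for what does count is the gap.

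**It is an exploratory pilot.** This softens the consequence. A reader might also infer that the next study could be built on a chance brain location, but Section 9.2 ties follow-up to a treatment effect, not to an imaging finding. Even so, hypothesis 6 has a formal H0 and H1 under the same 5% rule as the rest.

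**Conclusion.** The point holds in conditional form. The plan states no multiplicity correction for its voxel-wise test of hypothesis 6. If the 5% rule is applied to voxel-level p-values, and the regressor varies, the chance of at least one false positive is near 1 for any plausible search volume, with about 5% of voxels flagged per null map. That conclusion rests on assumed voxel size and search volume but is insensitive to them once there are about 60 effective tests.

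Separately, and with no assumption about images, the regression as literally written has a constant regressor and cannot test prediction of response.

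The documents do not show that uncorrected p-values will be used. Nor do they make perfusion the only admissible marker: the background in Section 2.1 singles out cerebral blood flow, but the synopsis and Section 4.1 list four modalities without ranking them.

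**What to change.** Amend Section 9.4.3, with a cross-reference from 9.4.1 so that the general 5% rule does not govern raw voxel p-values:

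1. **Outcome.** Replace baseline HCS with a response measure that varies, such as post-treatment HCS at a named time point. Include a term that separates real from sham (for example, an interaction between arm and imaging measure), so that prediction of response to stimulation is not confused with prognosis common to both arms.
2. **Threshold within each map.** Judge every imaging map at family-wise-error-corrected p<0.05, for example by permutation, which the plan already names for FA. State that uncorrected voxels do not support H1 of hypothesis 6.
3. **Multiplicity across maps.** Either name one imaging measure in advance as the test of hypothesis 6 (baseline rCBF is a candidate given Section 2.1, but the choice is the sponsor's), or correct across the modalities tested, for example 0.0125 each for four. Label the remaining maps exploratory.

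This is a change of wording: no new data, patients or visits, and permutation inference is already in the plan. The cost is that fewer regions will be reported as significant. The primary HCS comparison is not touched.
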